### 3.2 Contraindications to Efinaconazole administration

- Known hypersensitivity to efinaconazole

### 3.3 Benefits of Study

The potential benefits of treating onychomycosis have been well-documented; these benefits are only heightened in the setting of diabetes mellitus. A recent report investigated the impact of successful treatment with efinaconazole 10% solution among a group of subjects with onychomycosis. The study found a statistically greater improvement in all investigated aspects of quality of life compared to a controlled vehicle group (Tosti, 2014). Furthermore, the risk profile of the topical medication have been documented and represent qualitatively small levels of risk.

It is believed that the potential benefits of this study outweigh the potential risks.

## 4 SUBJECT SELECTION

Prior to enrollment, an informed consent must be obtained. Eligibility will be determined by the established inclusion and exclusion criteria. Assuming a 50% screen rate, it is anticipated that a total of 96 subjects will need to be screened to reach 48 intention-to-treat subjects. Using an estimate of 55% for mycologic cure, 48 subjects will yield a 95% confidence interval of 0.281.

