### **2.4.1 Primary Endpoints**

1. The primary efficacy end point will be the proportion of subjects achieving complete cure at week 50.

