### **5.2.3 Procedures**

- KOH wet mount and fungal culture at final office visit
- Additional safety laboratory studies will be ordered as needed
- Debridement of target toenail
- Debridement of other toenails as needed

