### ***6.3 Early Termination Appointment***

If the subject elects to discontinue the study prior to completion, the subject will be asked to attend an early termination appointment. This early termination appointment will replace the final office visit. It will include the procedures of a follow-up office visit, with the addition of a complete history and physical. Subjects will be provided increased, but not excessive, financial compensation as motivation for attending this appointment.

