## **7.1 Safety Evaluation**

Safety will be assessed by recording the nature, intensity, and duration of treatment related adverse events. Safety analyses will be performed on both an intention-to-treat and per-protocol analysis basis. The intention-to-treat population will include each patient receiving at least one dose of the medication, with at least one post-baseline assessment.

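### Does the plan have to change because it never states the denominator of the cure rates or how early leavers are counted?

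*Combined protocol and SAP*

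**What the plan says.** Section 4 gives the recruitment arithmetic, "Assuming a 50% screen rate, it is anticipated that a total of 96 subjects will need to be screened to reach 48 intention-to-treat subjects", and then the precision statement, "Using an estimate of 55% for mycologic cure, 48 subjects will yield a 95% confidence interval of 0.281".

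Section 2.4.1 defines the main result: "The primary efficacy end point will be the proportion of subjects achieving complete cure at week 50". Section 2.4.2 lists mycological cure among the secondary endpoints, with no time point. Neither section names an analysis population.

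Section 7.1 is the only place where populations are tied to an analysis: "Safety analyses will be performed on both an intention-to-treat and per-protocol analysis basis". It goes on: "The intention-to-treat population will include each patient receiving at least one dose of the medication, with at least one post-baseline assessment". Per-protocol is not defined.

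Follow-up mycology is listed in section 5.2.3 as "KOH wet mount and fungal culture at final office visit". For those who leave, section 6.3 says: "If the subject elects to discontinue the study prior to completion, the subject will be asked to attend an early termination appointment". It adds: "This early termination appointment will replace the final office visit". Section 6.1 counts a subject as a completer only after the week 50 evaluation. Section 10.5 requires missing data to be noted with a reason but gives no rule for analysing them.

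**The concern.** The study has no control arm (section 2.1), so the cure proportion is itself the result, and no comparison group absorbs a counting choice made once the data are known. Three choices seem open for a subject who leaves early: count as not cured, leave out of the denominator, or use the mycology from the early termination appointment. The first and third keep 48 in the denominator; the second does not.

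The situation can arise in practice. A subject with one dose and a week 10 visit is in the intention-to-treat population, yet may have no follow-up KOH or culture, because these are taken only at the last visit. Section 6.3 puts the early appointment in place of that visit, while section 2.4.1 fixes the primary endpoint at week 50. By its wording, section 6.3 covers only subjects who choose to stop. Those withdrawn for an adverse event or not located (section 6.2) may have no result at all. If many subjects left, the reported rate could depend noticeably on the choice.

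**Working it through.** **Inputs.** Rate 55%, n = 48, 95% confidence and 50% screen rate (section 4). Discontinuation for adverse events on efinaconazole 3.2% and 1.9% in the two phase III studies (section 1.4). The protocol gives no all-cause dropout rate, so 10 leavers of 48 (about 20%) is an assumption used only to show the range.

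**The plan's own figures.**
- Screening: 48 / 0.50 = 96.
- Full Wald width: 2 × 1.96 × √(0.55 × 0.45 / 48) = 0.2815, the stated 0.281. The half-width is 0.1407, or 14.1 points.

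**Likely number of leavers at the documents' rates.** 48 × 0.019 = 0.9 and 48 × 0.032 = 1.5, so 1 to 2 subjects.

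**Effect of the counting choice.** Let d of the 48 leave early and let 55% of the other 48 − d be mycologically cured.
- Not cured: 0.55(48 − d)/48
- Left out: 0.55, with width 2 × 1.96 × √(0.2475/(48 − d))
- Early result counted, upper bound (all attend, all negative): (0.55(48 − d) + d)/48

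| d | Not cured | Left out (width) | Upper bound | Lowest to highest, d/48 |
|---|---|---|---|---|
| 1 | 53.9% | 55.0% (0.284) | 55.9% | 2.1 points |
| 2 | 52.7% | 55.0% (0.288) | 56.9% | 4.2 points |
| 10 (assumed) | 43.5% | 55.0% (0.316) | 64.4% | 20.8 points |

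With 2 leavers counted as not cured, the width over 48 is 2 × 1.96 × √(0.527 × 0.473/48) = 0.282, practically the planned value.

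**When would the choice outweigh sampling error?** The gap between not cured and left out is 0.55d/48. At d = 12 it is 13.75 points and at d = 13 it is 14.9, so it passes the half-width of 14.1 only at 13 leavers. The extreme spread d/48 passes it at 7 (7/48 = 14.6 points; 6/48 = 12.5), but only if every leaver attends the early appointment and every one tests negative.

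**Primary endpoint.** The 55% is for mycologic cure. Complete cure also needs 0% nail involvement, so its rate p among those assessed cannot exceed the mycologic cure rate. The gap between not cured and left out is then p·d/48, which is no larger than the figures above while mycologic cure is 55%.

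**The case for a change.** The strongest case for acting is that the phase III rates cover adverse events only. Section 6.2 also foresees withdrawal and loss of contact over 50 weeks, and at an assumed 10 leavers the readings run from 43.5% to at most 64.4%. Even if 48 is accepted as the denominator, the numerator stays open: section 6.3 could be read as letting an early result stand in for the final one, while section 2.4.1 points to week 50. A sentence or two would settle this at no cost.

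Part of this stands. The protocol does leave the scoring of early leavers and the per-protocol set unstated, and all-cause loss could exceed 3.2%. But the wide spread needs both an assumed loss rate and the extreme that all leavers attend and test negative. Attendance is only requested, and those withdrawn for adverse events or not located fall outside the wording of section 6.3. Nor does section 6.3 give an analysis rule: it describes how a visit is conducted.

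A related worry, that 96 allows no loss between eligibility and the first post-baseline assessment, does not hold up. The screen rate may equally mean the share of screened subjects who reach the intention-to-treat population. In either case sections 2.2 and 2.3 keep enrolment open until 48 are reached.

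**Conclusion.** This is missing detail that an analyst fills sensibly. Section 4 speaks of 48 intention-to-treat subjects and in the next sentence computes the interval on 48. With the definition in section 7.1, the natural reading is that cure rates are taken over that population. Read with the week 50 time point in section 2.4.1, a subject without a week 50 result has not been shown to be cured then. That reading keeps the denominator at 48 and the width at about 0.28.

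No stated number or rule is shown to be wrong. At the only loss rates in the documents the choice moves the mycologic cure rate by 2.1 to 4.2 points at most, against a half-width of 14.1. The two readings that need no early mycology differ by more than the half-width only from 13 leavers of 48. The study is described as a pilot (section 8), with no hypothesis test or success threshold that a few points could tip.

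The conclusion assumes that loss stays moderate, and that the report gives the number of early leavers and the denominator used. Section 10.5 already requires the reasons for missing data to be recorded, so a reader could recompute the rate on another basis.

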#### **4.1 Informed Consent/Screening Visit**

Subjects will complete a written informed consent prior to enrollment. This will be administered by the investigators at the study site in the patient's preferred language (English or Spanish). The informed consent must be signed and dated. Each subject will be assigned a number in ascending order beginning from 01. A screening log of all the subjects will be obtained for each written informed consent. The screening log includes: screening number, first and last name, age, gender, eligibility status or reason for ineligibility. This information will be stored in a locked security box, and kept in a locked cabinet at the Arrowhead Regional Medical Center. This will be accessible only by specifically designated study personnel.

##### **4.1.1 Medical History Screening**

Subject eligibility will be determined by the inclusion/exclusion criteria. Record if the subject does or does not meet the criteria.

1. Record date of visit, subject enrollment number, and subject initials
2. Verify subject eligibility based on inclusion and exclusion criteria. Adherence to criteria will be noted.
3. Record subject demographics, including date of birth, gender, race, and weight, and if there were any treatments attempted prior to enrollment.

##### **4.1.2 Physical Assessment Screening**

Subject eligibility will be determined by the inclusion and exclusion criteria. Subject adherence to inclusion or exclusion criteria will be recorded. Screening will include reviewing and obtaining informed consent, reviewing inclusion/exclusion criteria, and the initial (complete) physical examination.

###### **4.1.2.A Criteria for Diagnosis of Onychomycosis**

To establish diagnosis, a positive potassium hydroxide (KOH) wet mount is required, along with a fungal culture positive for a dermatophyte species.

#### **4.2 Inclusion Criteria**

To be considered for inclusion, clinical diagnosis will need to be confirmed through positive KOH stain or positive mycologic culture findings. Involvement of at minimum 20% of the target great toenail will be required for inclusion. A negative pregnancy screen will be required among women of child-bearing age. These women will be required to be on oral contraceptive throughout the study duration.

Subjects will be recruited from Arrowhead Regional Medical Center.

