## **2.2 Treatment Groups**

Adult subjects (18 years or older) with a medical history of controlled type 2 diabetes mellitus will be considered for enrollment. Subjects will be eligible for enrollment if a clinical diagnosis of distal onychomycosis involving at least 20% of one great toenail (GT) has been made and confirmed by nail biopsy. There will be no restriction based on nail involvement; up to 100% of the nail may be involved. Furthermore, there will be no restriction based on toenail plate thickness. The enrollment period will be continued until 48 intention-to-treat subjects have been enrolled in the study.

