#### **4.4 Method of Subject Assignment to Treatment Groups**

Subjects will be enrolled into the study after verification of eligibility according to the inclusion and exclusion criteria. Written informed consent will also be obtained from subjects.

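### Section 4.1.2.A requires both mycology tests positive at entry, section 4.2 accepts either one, and nothing says which prevails, so what the mycological cure rate measures depends on the rule applied.

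*Combined protocol and SAP*

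**What the plan says.** The entry rule for mycological confirmation appears in three places in the combined protocol and SAP.

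- Section 4.1.2.A (diagnosis of onychomycosis): "a positive potassium hydroxide (KOH) wet mount is required, along with a fungal culture positive for a dermatophyte species". Both tests must be positive, and the culture must grow a dermatophyte.
- Section 4.2 (inclusion criteria): "clinical diagnosis will need to be confirmed through positive KOH stain or positive mycologic culture findings". Either test is enough, and this sentence does not restrict the species.
- Section 2.2 (treatment groups): the clinical diagnosis "has been made and confirmed by nail biopsy". This may only describe how the specimen is taken, but the text does not say so.

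Several sections name the inclusion and exclusion criteria as the eligibility check. Section 4 says "Eligibility will be determined by the established inclusion and exclusion criteria", section 4.1.1 says "Subject eligibility will be determined by the inclusion/exclusion criteria", section 4.1.2 says "Subject eligibility will be determined by the inclusion and exclusion criteria", and section 4.4 says "Subjects will be enrolled into the study after verification of eligibility according to the inclusion and exclusion criteria". Section 5.1.2 repeats the instruction at the initial visit. None of them mentions 4.1.2.A. Section 5.1.1 sends the reader to section 4 as a whole, which contains both rules.

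Section 2.4 defines mycological cure as a negative KOH and a negative culture of the target toenail. Complete cure, the primary endpoint in 2.4.1, is mycological cure plus 0% nail involvement.

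**The concern.** The same subject can be eligible under one section and ineligible under another. Staff working from 4.2 would enrol someone with a positive KOH and a negative culture. Staff working from 4.1.2.A would reject that person.

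The choice of rule changes what the cure rate measures. If both tests are positive at entry, mycological cure requires two conversions. If only one is positive, it requires one conversion, and the test that was negative at baseline counts toward cure if it is still negative at the final visit. Section 2.1 describes the study as uncontrolled, so no comparison group would separate this from a treatment effect.

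There is also a species problem. Section 4.3 excludes nondermatophyte infection, but a subject admitted on KOH alone has no cultured organism against which to check that exclusion. Section 1.5 gives the indication as two named dermatophytes.

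**Working it through.** **The plan's own figures.** Section 4 gives 48 subjects, an assumed mycological cure rate of 55%, a 95% interval of 0.281 and a 50% screen rate.

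- Full interval width: 2 × 1.96 × √(0.55 × 0.45 / 48) = 0.281. The half-width is 14.1 points.
- Screening: 48 / 0.50 = 96.

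Both figures reproduce. The width depends only on the assumed rate and the sample size, so it is the same under either entry rule. The screening number is not: "Assuming a 50% screen rate, it is anticipated that a total of 96 subjects will need to be screened" does not say which rule the 50% refers to.

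**Status at entry against the definition of cure.**

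| Baseline result | Eligible under 4.1.2.A | Eligible under 4.2 | Tests that must convert for mycological cure |
|---|---|---|---|
| KOH positive, dermatophyte culture positive | yes | yes | two |
| KOH positive, culture negative | no | yes | one |
| KOH negative, dermatophyte culture positive | no | yes | one |

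**Direction.** Needing only one conversion pushes the rate up. Admitting subjects with no identified dermatophyte could push it down, given the indication in 1.5. The documents give no share of single-positive subjects, no test error rates and no cure rates by baseline status, so the net direction cannot be settled.

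**Scale, under assumptions.** Let *s* be the share of enrolled subjects positive on only one test, and *d* the difference in mycological cure rate, single-positive minus both-positive. The overall rate differs from the both-positive rate by *s* × *d*. Neither value comes from the documents.

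| *s* (assumed) | *d* = ±10 points | *d* = ±20 points | *d* = ±30 points |
|---|---|---|---|
| 10% | ±1 | ±2 | ±3 |
| 20% | ±2 | ±4 | ±6 |
| 40% | ±4 | ±8 | ±12 |

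**Screening, with the same assumed shares of 10%, 20% and 40%.**

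- 50% rate assumed either test, both tests applied: 48 / (0.5 × (1 − *s*)) = 106.7, 120, 160, so 107, 120 or 160 screened.
- 50% rate assumed both tests, both tests applied: 96.
- 50% rate assumed both tests, either test applied: 48 × (1 − *s*) / 0.5 = 86.4, 76.8, 57.6, so 87, 77 or 58 screened.

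**The case against.** The strongest reply is that the two rules can both be obeyed. Section 4.2 sets a minimum, 4.1.2.A states what establishes the diagnosis, and a careful site following both would require both tests. Section 5.1.1 points to all of section 4, and 4.1.2.A sits directly under 4.1.2, one of the sections said to bypass it. The nondermatophyte exclusion also fits a dermatophyte culture at entry. On this view the problem is a drafting slip, and bias arises only if 4.1.2.A is ignored.

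The joint reading is available, but the plan does not state it. If both tests are intended, the alternative in 4.2 is wrong as written, and 4.2 is the list that staff are repeatedly told to check. If 4.2 is intended, the requirement in 4.1.2.A is contradicted.

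Other parts of the reply stand:

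- Nail biopsy may describe the specimen and need not be a third rule.
- The eligibility check in 5.2.1 concerns follow-up visits and says little about entry.
- A single-positive subject must still convert the positive test to count as cured.
- The downward mechanism is only a possibility, because the documents give no efficacy by species and 4.1.2.A itself accepts any dermatophyte.
- The shares and differences used above are assumptions, and every resulting shift is below the planned half-width.

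These points limit how much can be said about size. They do not remove the conflict.

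**Conclusion.** The concern holds and should be fixed. Sections 4.1.2.A and 4.2 state different entry rules, and no section says which governs. Confidence is high on the conflict and on how it reaches the endpoint. It does not extend to the size or sign of the effect, which the documents cannot supply.

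Mycological cure, a secondary endpoint and the one used for the precision statement, is most exposed. Treatment success and complete cure contain mycological cure and are affected too, but less, because they also need at most 10% or 0% involvement from an entry minimum of 20%. A shift smaller than the half-width still matters, because it would be systematic and the confidence interval would not reflect it.

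**What to change.** Reconcile sections 2.2, 4.1.2.A and 4.2 into one entry rule. The simplest way is to make 4.2 match 4.1.2.A: a positive KOH and a culture growing a dermatophyte, both from the target great toenail at screening. State in 2.2 whether nail biopsy means that specimen, and state in section 4 which rule the 50% screen rate assumes.

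This is a wording change, since 4.1.2.A already names both tests. It needs no extra screening if the 50% rate assumed both tests. If it assumed either test, screening rises above 96 by 11%, 25% or 67% at assumed single-positive shares of 10%, 20% or 40%.

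If either test is to suffice, require both to be done and recorded at screening for every subject. The list of screening contents in 4.1.2 names no mycology, and section 5.1 as available lists no baseline KOH or culture, so this needs to be explicit. Then prespecify that mycological cure, treatment success and complete cure are also reported for subjects positive on both tests at baseline, as a supplement to the main analysis. The cost is precision: at the same shares the subset is 48 × (1 − *s*), about 43, 38 or 29 subjects, with interval widths of 0.30, 0.32 or 0.36 at a 55% rate, against 0.281 for all 48.

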#### **4.3 Exclusion Criteria**

Subjects will be excluded if any of the following exclusion criteria are met:

- Diagnosis of a nondermatophyte fungus infection, diagnosis of proximal subungual onychomycosis, diagnosis of superficial white onychomycosis
- Diagnosis of peripheral arterial disease or anatomic abnormalities of the target toenail
- Inability to follow through with all requisite office visits
- Routine use of a systemic corticosteroid, routine use of a systemic immunomodulator, or history of systemic antifungals within the prior five years.
- Active interdigital tinea pedis refractory to topical antifungal treatments
- Known hypersensitivity to efinaconazole
- Use, within the month preceding screening, of: topical antifungal agents, topical anti-inflammatory agents to the toes
- Any history of oral systemic antifungal with known activity against dermatophytes

#### **4.4 Method of Subject Assignment to Treatment Groups**

Subjects will be enrolled into the study after verification of eligibility according to the inclusion and exclusion criteria. Written informed consent will also be obtained from subjects.

## **5 STUDY PROCEDURES**

## **5.1 Initial Visit**

### **5.1.1 Enrollment**

Refer to section 4.

### **5.1.2 Medical History**

1. Record date of visit, subject enrollment number, and subject initials.
2. Verify subject eligibility based on inclusion and exclusion criteria. Adherence to criteria will be noted.

### **5.1.3 Physical Examination**

- The complete history and physical will be performed at screening. At the first visit, the examination will be limited to a problem focused examination.
- Digital assessment of the great toe/planimetry.
- Vital signs.
- Clinical assessment of the toenails.

### **5.1.4 Procedures**

#### **5.1.5 Adverse Events Pre-screen**

Subjects' health status will be studied for the purpose of recording adverse events in the future.

#### **5.1.6 Treatment**

- Eligible subjects will be given efinaconazole 10% solution, and instructed to apply the solution to the great toenail (GT). If more toenails are affected, the solution may be applied in the same manner to all affected toenails as directed by the investigator and desired by the patient.

## **5.2 Follow-up Visits**

Subjects will be assessed at the screening, at baseline, and at every 10 weeks until week 50 (at weeks 10, 20, 30, 40, and 50). The final assessment (week 50) will include a complete history and physical examination, replacing the lower extremity focused physical examination.

